There is potential benefit to introducing palliative care earlier in the course of illness for patients with chronic liver disease. For some patients with cirrhosis, palliative care has been shown to improve physical and emotional symptoms. In a recent observational study, Baumann et al found that for patients with ESLD on the waiting list for liver transplant, an early PC intervention counteracted the progression of worsening symptoms and significantly improved pruritus, appetite, anxiety, depression, fatigue, and well-being.¹⁴

In addition to quality of life, hospital utilization for hepatic patients is of particular concern. Hospital admission rates and the economic burden of treating these patients have continued to rise.¹⁵ In a study of 402 patients with decompensated cirrhosis who were admitted to hospital, 78% of patients had at least one readmission, with 14% of these patients readmitted within 1 week after discharge at a mean cost of \$25,898 per readmission. Another 37% of these patients were readmitted within 1 month after discharge at a mean cost of \$20,581 per admission. Of these, 22% were determined to be possibly preventable admissions.¹⁶

Palliative Care interventions have been shown to reduce hospital utilization for some liver transplant service patients. Lamba et al conducted a prospective observational study comparing outcomes before and after structured palliative care program integration in the surgical intensive care unit for liver transplant service patients. After program implementation, goals of care discussions during physician rounds increased significantly (from 2% to 39% of patient-days), and the mean length of stay in the SICU decreased by 3 days for patients who died and by 4 days for patients who survived. Although mortality rates were similar pre- and post- program implementation, DNR status significantly increased in those who died from 52% pre-implementation to 81% post-implementation. DNR status was also instituted earlier, decreasing from 38 days after admission to 19 days after admission.¹⁷ Palliative care, once understood and integrated, has the potential to improve clinical outcomes, improve patient's quality of life, and reduce cost. But *when* to integrate the services, *how* to integrate services, and *for which* patients, is not well established.

Resistance and Conceptual Barriers

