5.0 Participant Selection

Approximately 400 adult hepatology patients with poor prognosis (identified by the ‘surprise question’ see below) will be randomized to receive either usual hepatic care (control group, N=200) or usual hepatic care with comprehensive palliative care services (intervention group, N=200). Any Vanderbilt patient admitted to the primary inpatient service of one of the study hepatologists with limited life expectancy may be eligible for participation. We expect a participation rate of ~75% (based on the participation rate of a similar study conducted by [name]), and no more than 10% of patients excluded based on eligibility criteria. We are powered to detect a 13% difference in readmission rate between treatment arms with 400 participants, assuming equal mortality across arms (see section 8.0, Statistical Analyses). As this is an internally funded study, we will have flexibility to enroll patients past the the accrual goal of 24-months in order to enroll 400 participants if necessary.

Inclusion Criteria:

- Inpatient at Vanderbilt University Medical Center with advanced liver disease, whose treating hepatologist indicates a ‘No’ response to the question, “Would you be surprised if this patient died within 1 year?”

Exclusion Criteria:

- Age < 18 years
- Inability to give written informed consent (patient or surrogate decision-maker)
- Inability to respond to questions in English
- Treating hepatologist denies permission to enroll
- Receiving hepatology care at non-Vanderbilt sites (to ensure appropriate follow-up)

Recruitment

Potential patients will be identified within StarPanel using hepatology service codes and/or attending physician name. Patients’ electronic medical records will be manually reviewed by study personnel to confirm preliminary eligibility. Once preliminary eligibility is established, the treating hepatologist will receive a prompt via email with a REDCap survey link to respond to the question, “Would you be surprised if this patient died within 1 year?” The ‘surprise question’ has been used in a variety of patient populations for prognosis and to evaluate appropriateness for palliative care^{25,26} and has shown specificity (69.3%) and

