If the patient does not have the capacity to give written informed consent due to his/her current health state, the surrogate will provide written informed consent prior to the patient's enrollment in the study. The patient will be re-evaluated periodically for the capacity to give consent. The SC will confirm with the treating hepatologist if the patient is capable of providing written informed consent while inpatient. If the patient is found capable, the study coordinator will obtain written informed consent from the patient. If the patient is found to be capable, but is discharged prior to providing written informed consent, the study coordinator will contact the patient by telephone. The patient will sign the e-consent form in a similar manner as the surrogate decision-maker e-consent procedures described above. If the patient does not have access to a computer, and the patient provides verbal permission, a paper informed consent form for the patient to sign and return, a blank copy for the patient to keep, and a stamped addressed envelope to return the signed copy will be mailed to the patient. If the patient is found capable and declines participation, the patient and surrogate will be immediately terminated from the study. Study staff will print a copy of the signed document, and give to participant at time of study visit. Should a participant choose to receive a link to the consent document in lieu of a hard copy (or if they sign electronically from a remote location), they will receive a link to a ROCKET site containing the consent form appropriate to the version date that they signed. Signed consent documents will NOT be housed electronically on ROCKET. No research procedures will be performed until after consent has been provided.

After written informed consent is provided by the patient or surrogate, baseline measures will be completed, and patients will then be randomized (stratified by treating hepatologist) to the control or intervention arm using validated computer programs (**see Figure 3**). If the surrogate decision-maker provided consent for

the patient, patients will be randomized, but baseline measures will be completed by the patient after providing written informed consent. A panel within the EMR containing all enrolled patients and the arm assignment will be created and shared with the PC team.

[figure not shown]

Figure 3. Approach for Study Participant Selection

Caregiver Participation

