6.0 Intervention

We will conduct a randomized, controlled study to evaluate the impact of systematic, comprehensive palliative care services vs. usual hepatic care. After providing written informed consent, patients will complete baseline measures including demographic (**Appendix C**), mood, and quality of life questionnaires on the inpatient unit. Patients will be randomized to either the control (usual hepatic care) or the intervention arm (usual hepatic care with comprehensive palliative care services). Patients who are randomly assigned to usual care will not be scheduled to meet with the palliative care service unless a meeting is requested by the patient, the family, or the treating physician.

Patients randomized to the intervention arm will receive a binder (**Appendix D**) of patient materials including general information about palliative care services, the COMPASS study, and templates to document information if the patient wishes (names of medicine, upcoming appointments, important contact information, etc.). Intervention patients will also receive , contact information printed on a magnet (**Appendix F**), a wallet card (**Appendix G**), and a one-page handout (**Appendix H**). A VUMC palliative care physician or nurse practitioner will meet with the patient and appropriate surrogate, caregiver, family members, etc. after randomization to provide a verbal overview detailing palliative care services and to provide the comprehensive initial consult. Appropriate palliative care providers will provide follow-up in-person consults while the patient remains inpatient per usual palliative care services.

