Assess physical and mental functioning	X	X
Review and complete Advance Directives including: review of previously completed advance care directives, discussion/ completion of POST form, code status, and advance care directives (power of attorney, living will, or advance care plan)	X	X
Name surrogate	X	
Review medical history	X	
Review family history	X	
Review social history (marital status, tobacco use, smoking, alcohol use, drug use, occupation, children) and identify patient's barriers to healthcare access	X	
Dignity and Spirituality assessment (referral to chaplain where applicable)	X	X
Review medications and allergies	X	X
Review symptoms*	X	X
Explain medical condition/diagnosis in lay terms and discuss patient's understanding of prognosis	X	
Discuss questions to ask hepatologist	X	X
Discuss social/family support system	X	X
Develop Care Plan and Goals of Care in the context of the patients current medical condition	X	
Review Care Plan and Goals of Care in the context of the patients current medical condition	X	X
Direct/refer patient towards appropriate resources (e.g. hospice where applicable)	X	X
Record time spent with patient	X	X
Ensure family awareness as applicable	X	X
Communication of Care Plan and pertinent information back to Hepatology MD	X	X

*Symptoms include: lack of energy, lack of appetite, pain, dry mouth, weight loss, drowsiness, shortness of breath, constipation, diarrhea, difficulty sleeping, nausea, vomiting, fever, chills, sweats, sore throat, headaches, change in vision, polyuria, polydipsia, cold/heat intolerance, cough, hemoptysis, chest pain, palpitations, orthopnea, hematuria, renal stones, melena, anorexia, enlarged lymph nodes, bleeding, easy bruising, rhinitis, skin reactions, joint pain/swelling, weakness, myoclonus, sadness, agitation, anxiety, confusion, rash

Outcomes

Primary clinical endpoint:

- Time to first hospital readmission within 1-year post randomization

Secondary outcomes are expected to include:

- Days alive out of hospital within 6-months post randomization
- Total days in hospital within 1-year post randomization
- Total days in ICU within 1-year post randomization
- Number of hospital admissions within 1-year post randomization
- Cost of hospital admissions within 1-year post randomization
- Median length of stay per admission
- Number of transfers to hospice within 1-year post randomization
- Time to hospice
- Liver disease-specific health-related quality of life
- Generic measures of quality of life

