Aim 1: Time to first hospital readmission within 1-year post randomization will be compared across treatment assignment using Cox proportional hazards model, accounting for the competing risk of death and adjusting for relevant demographic and clinical characteristics. A less than 1 hazard ratio for the treatment group status implies reduced readmission rates in the intervention arm given equal mortality rates.

Aim 2: Days alive out of hospital within 6-months post randomization, total days in hospital and ICU within 1-year post randomization, number and cost of hospital admissions within 1-year post randomization, median length of stay per admission, number of transfers to hospice within 1-year post randomization, time to hospice placement after referral, survival, presence of advance directives within 1-year post randomization, presence of physical symptoms, transplant status listing (deferred, listed, declined), and number of completed liver transplants will be obtained via chart review and compared across treatment assignment using proportional odds model for ordinal outcomes, Cox proportional hazards model for time-to-event outcome and logistic regression for binary outcomes, adjusting for relevant demographic and clinical characteristics.

Aims 3 and 4: Both cross-sectional and longitudinal analysis will be conducted to compare between group differences in CLDQ. For the cross-sectional study, for each time point of data collection, linear regression with ordinary least square will be used with CLDQ as the dependent variable (DV) and treatment assignment (0 for control arm and 1 for the intervention arm) as the independent variable (IV) of interest adjusting for baseline CLDQ and potential confounding factors based on clinical and statistical considerations. A positive value of the regression parameter for treatment status indicates higher CLDQ in the intervention arm. For longitudinal analysis, linear mixed model will be adopted including follow-up time and the interaction between follow-up time and treatment group on top of the cross-sectional model. The interaction term is included to compare decreasing rate of CLDQ between groups with a positive value of the corresponding regression parameter indicating slower decline rate of CLDQ in the intervention arm.

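### Aim 1 reads a hazard ratio below 1 as reduced readmission, but time from randomisation also contains the remaining index stay, which can differ by arm

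*Combined protocol and SAP*

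**What the plan says.** - **Population.** Section 5.0 requires the patient to be an "Inpatient at Vanderbilt University Medical Center with advanced liver disease".
- **Randomisation.** In the usual path, section 5.0 says that after consent "baseline measures will be completed, and patients will then be randomized". Section 6.0 places the baseline work, including "mood, and quality of life questionnaires on the inpatient unit", so randomisation normally falls within the index stay.
- **Intervention.** It starts in that same stay. Section 6.0 describes an initial consult after randomisation and then: "Appropriate palliative care providers will provide follow-up in-person consults while the patient remains inpatient per usual palliative care services".
- **Endpoint and model.** Sections 2.0 and 6.0 time the endpoint from randomisation; section 6.0 lists it as "Time to first hospital readmission within 1-year post randomization". Section 8.0 does the same: "Time to first hospital readmission within 1-year post randomization will be compared across treatment assignment using Cox proportional hazards model". Death is to be handled as a competing risk.
- **Reading rule.** Aim 1 then says that an HR below 1 means fewer readmissions under intervention, provided mortality is equal. It states no other condition.
- **Data.** Section 7.1 collects hospital admission and discharge dates as primary outcome data.

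The available text of Aim 1 does not mention index discharge, the stay remaining after randomisation, or patients who are never discharged.

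**The concern.** A patient cannot be readmitted before being discharged. The days from randomisation to index discharge therefore carry no risk of the event, yet they count towards the time to event. They come after randomisation and are exposed to the intervention, so randomisation does not make them equal between arms.

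An arm difference is plausible on the plan's own background. Section 1.0 cites a study of structured palliative care for liver transplant service patients in which "the mean length of stay in the SICU decreased by 3 days for patients who died and by 4 days for patients who survived". The background also puts many readmissions in the first week and month after discharge, where a shift of a few days has most effect.

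What is at stake is interpretation. An intervention that sends patients home earlier, with no change in what happens afterwards, would look slightly worse on the primary endpoint. One that kept them in longer would look slightly better. The Aim 1 sentence would call either result a change in readmission.

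**Working it through.** **1. The plan's own figure.** Table 3 was checked first, with total events = 400 × R, two-sided alpha 0.05 (the plan does not state sidedness), power 80% and 1:1 allocation. By Freedman's formula, events = (1.96 + 0.84)² × [(1 + HR)/(1 − HR)]² and N = events/R. For R = 60% and HR 0.69: 7.85 × (1.69/0.31)² = 233.3, rounded up to 234 events; 234/0.60 = 390. Solving at N = 400 gives HR 0.669, 0.694, 0.713, 0.729 and 0.743 for R = 50 to 90%. All five match the table (0.67, 0.69, 0.71, 0.73, 0.74). The point disputes none of these figures.

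**2. The mechanism.** Let L be the days from randomisation to index discharge, G the days from discharge to readmission, and D the days to death. The analysed time is T = L + G, with an event if T ≤ 365 and T < D. If G and D have the same distribution in both arms but L does not, T differs between arms and the HR is not 1. Equal mortality fixes only D.

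**3. Size, first set of assumptions.**
- L: gamma (shape 1.5), mean 8 days in control (assumed; not in the documents).
- D: exponential, 50% dead at 1 year in both arms (section 8.0).
- G: Weibull, shape 0.74. It is fitted to the background cohort's early readmissions, read as 14% and 37% of the 78% readmitted: 0.78 × 14% = 11% at 1 week and 0.78 × 37% = 29% at 1 month. It is then scaled to the pilot's 62% at 1 year. The pilot counts from the qualifying admission, so this scaling is approximate.
- N = 200 per arm. Power is at a true post-discharge HR of 0.69.

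| Mean remaining stay, intervention | Null HR from randomisation (subdistribution) | Power from randomisation: subdistribution / cause-specific | Power from discharge: subdistribution / cause-specific |
|---|---|---|---|
| 10 days | 0.984 | – | – |
| 8 days | 1.003 | 72.5% / 79.1% | 73.0% / 79.1% |
| 6 days | 1.015 | 69.4% / 77.4% | 73.6% / 80.0% |
| 4 days | 1.035 | 66.0% / 73.8% | 73.3% / 79.7% |

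The equal-stay row should read 1.000, so simulation noise is a few thousandths. A stay 4 days shorter costs 72.5 − 66.0 = 6.5 points (subdistribution) or 79.1 − 73.8 = 5.3 points (cause-specific). Repeat runs gave null HRs of about 0.99, 1.01 and 1.03 for 10, 6 and 4 days, and a loss of 6 to 8 points for 4 days. Only the fall in power matters here, because the starting level depends on the assumed model.

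**4. Size, second set of assumptions.** Control mean 10 days; mortality 35% or 50%; readmission 50%, 62% or 70%; constant or front-loaded readmission hazard.

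| Mean stay, control v intervention | Null HR from randomisation | One-sided false finding (nominal 2.5%) |
|---|---|---|
| 10 v 7 or 6 days | 1.02 to 1.05 | harm: 3.0 to 5.9% |
| 10 v 14 days | 0.96 to 0.98 | benefit: 3.1 to 6.0% |

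Timed from discharge, the null HR was 1.00 throughout. With a true effect on time after discharge (HR 0.62, about 60% readmitted, 50% mortality), a stay 3 to 4 days shorter cost about 3 to 4 points of power (87% to 84%, or 90% to 86%).

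**5. Outer edge.** Using the background cohort's early rates unscaled (74% readmitted at 1 year), a stay 4 days shorter takes power from 78% to 69%. Other readings of that cohort's percentages give null HRs of 1.05 to 1.08 for 4 days. These rest on an outside cohort rather than the pilot and are not used as the estimate.

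**The case against.** **Time zero is correct.** A reader might infer that the clock should start at discharge. The documents do not support that. Randomisation is the intention-to-treat origin and is stated consistently. A from-discharge comparison conditions on leaving hospital alive, which is itself a post-randomisation event. It looked clean above only because discharge was simulated as unrelated to prognosis. With a shared frailty and about 11% index-stay deaths (both assumed), its null HR drifted to 1.01 to 1.04. The from-randomisation HR drifted more in those runs (1.03 to 1.14). The from-discharge analysis is therefore informative but cannot arbitrate. This objection stands in full.

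**The background figure does not transfer.** It is surgical ICU stay, in transplant service patients, before and after a programme. It is not the hospital stay remaining after randomisation on a hepatology service. It shows that an arm difference is plausible, not how large it would be. Nothing in the documents suggests that palliative care delays discharge, so a false benefit by that route is only a formal possibility. This also stands.

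**Secondary outcomes would show earlier discharge.** Aim 2 has total hospital days, days alive out of hospital, admission counts and median stay per admission. An earlier-discharge benefit would probably be visible there. None of these isolates the index stay, however, and none corrects the Aim 1 reading rule. This stands only in part.

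**Not every patient is an inpatient at randomisation.** Section 7.2 allows baseline questionnaires by telephone after discharge, so exceptions are possible. Inpatient randomisation remains the usual path.

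**Conclusion.** The point holds as a gap in interpretation, not as a fault in the choice of time zero. Equal mortality is not enough for an HR below 1 to mean reduced readmission after discharge, because the measured time includes a stretch of hospital stay that the intervention can alter.

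The size is modest. With assumed mean remaining stays of 8 to 10 days in control, a difference of 2 to 4 days moves the null HR by about 1 to 5%, and a stay 4 days shorter costs roughly 3 to 8 points of power. The design HRs are 0.67 to 0.74, so a shift of this kind could blur a borderline result but could not by itself produce an effect of the planned size. The stay lengths and their differences are assumptions; a larger arm difference would matter more.

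Two stronger readings are not supported. One is that the primary endpoint is invalid. The other is that a patient who dies without leaving hospital is always scored as a long readmission-free record. In a cause-specific Cox model that patient is censored at death. In a subdistribution model the patient stays in the risk set, but so does everyone who dies before readmission.

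**What to change.** Keep the comparison from randomisation as primary. In section 8.0, Aim 1, before results by arm are seen:

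1. Add one pre-specified sensitivity analysis: the same model, with the clock or risk-set entry starting at index discharge, labelled as conditional on live discharge.
2. Report by arm the days from randomisation to index discharge and the number of deaths before index discharge.
3. Replace the reading sentence. Suggested wording: *A hazard ratio different from 1 indicates a change in time from randomisation to first readmission, which may include a difference in index-stay length. It will be interpreted together with the analysis from index discharge and with index-stay length and index-stay deaths by arm. If the two analyses point in different directions, the result will be described as not separable from index-stay length. The sensitivity analysis does not overrule the randomised primary result.*

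The cost is a few sentences and one extra model on the dates already collected under section 7.1, with no change to N = 400. The downside is that the added analysis conditions on a post-randomisation event, so it must remain supportive.

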7.0 Data collection

7.1 Primary Outcome Data

Primary outcome data (hospital admission and discharge dates) will be obtained for this study through retrospective chart review utilizing StarPanel and the Research Derivative (RD). The RD is a database of clinical and related data derived from the Medical Center's clinical systems and restructured for research. Data is repurposed from VU's enterprise data warehouse, which includes data from StarPanel, VPIMS, and

ORMIS (Operating Room Management Information System), EPIC, Medipac, and HEO among others. The medical record number and other person identifiers are preserved within the database. Data types include reimbursement codes, clinical notes and documentation, nursing records, medication data, laboratory data, encounter and visit data, among others. Output may include structured data points, such as ICD 9 codes or encounter dates, semi-structured data such as laboratory tests and results, or unstructured data such as physician progress reports. The database is maintained by the Office of Research Informatics under the direction of [name].

